Title

Effects on muscle strength after blood flow restriction resistance exercise (BFR-RE) in early in-patient rehabilitation of chronic obstructive pulmonary disease acute exacerbation (COPDAE), a single blinded, randomized controlled study

NCT number: NCT04448236

Last updated on 8th July, 2020

Introduction

Chronic obstructive pulmonary disease (COPD) is a prevalent disease around the world particularly in developed countries. COPD often has frequent admissions for acute exacerbation which increase the risks of mortality. Muscular dysfunction is one of extra-pulmonary morbidity of COPD (Jaitovich, 2018).

Reduced muscle strength is associated with increased mortality in moderate to severe COPD (Swallow, 2007). However, at least 70% of 1-repetitive maximum of weight is needed to achieve muscle growth in resistance training (ACSM, 2009). This might not be feasible particularly to the patients admitted for COPD acute exacerbation (COPDAE).

Blood flow restriction resistance training (BFR-RE), Kaatsu training, was developed by [name] more than 40 years ago (Sato, 2005). The basic physiological mechanism of BFR-RE to increase muscle mass and strength is by metabolite accumulation, e.g. lactate. The metabolites lead to increase of serum growth hormone (GH) which promotes the collagen synthesis for tissue repair and recovery. The surge of GH leads to release of insulin-like growth factor (IGF-1) which is a protein related to muscle growth. IGF-1 contributes the muscle gain, which is a muscular anabolic process, by enhancing satellite cell proliferation. (Manini, 2009)

Concerning growth of muscle mass, BFR-RE leads to a comparable increase when compared to high load resistance exercise (HL-RE) (Lixandrão, 2017). However, concerning increase of muscle strength, BFR-RE is less effective in gain than that in HL-RE but more effective than that in low load resistance exercise (LL-RE) alone. Therefore, BFR-RE can be considered when HL-RE is not advisable. (e.g. frail elderly, post-operative rehabilitation, etc.)

BFR-RE is well studied among healthy adult (Lixandrão, 2017), elderly (Centner, 2019) and musculoskeletal rehabilitation patients (Hughes, 2017), but not in COPDAE patients.

Standardized isotonic knee extension resistance training on alternate day with a load of 15-30% of 1-repetition maximum (1-RM) with “BFR-device” will be compared with the control arm having same set of training without the device in COPDAE patient during 2-week of inpatient stay.

Though there no adverse risk responses were reported in published

randomized controlled trials in clinical populations in the literature, there are some expected transient perceptual type responses, e.g. dizziness, limb numbness, perceived exertion, delayed onset muscle soreness. There are no significant risks of complications if BFR-RE is prescribed by certified trainers who have knowledge of appropriate protocols and contraindications to the use of occlusive stimuli. (Brandner, 2018)

The effect on muscle strength in COPDAE inpatients, which is not well studied in the literature, will be the primary outcome of this study. The effect on mobility functions, systemic muscle strength reflected by hand grip strength, health related quality of life and unplanned readmission rate within 1 month of discharge for COPDAE will be evaluated as secondary outcomes. Since BFR-RE is newly introduced to Haven of Hope Hospital and not widely used in Hospital Authority, acceptability and feasibility of this training will be explored as secondary outcomes.

Subjects

Patients with COPD acute exacerbation (COPDAE) will be recruited to find out the effect of blood flow restriction resistance exercise (BFR-RE). There will be a control group without BFR-RE for comparison. Principal investigator will screen the medical fitness of the subjects before recruiting to the study.

Inclusion criteria

1. COPD acute exacerbation (COPDAE) as the primary diagnosis for hospitalization or transfer to pulmonary wards of the Haven of Hope Hospital
2. Able to walk under supervision
3. Understand instruction in Cantonese and can give informed consent.

Exclusive criteria (Hick, 2013)

Subjects will be excluded if they have any of the following conditions:

1. Concomitant acute cardiac event	7. History of lymphectomies
2. Severe hypertension (BP > 180/100)	8. Extremities with dialysis access
	9. Vascular grafting

3. History of venous thromboembolism
4. History of peripheral vascular disease
5. Absence of posterior tibial or dorsalis pedal pulse
6. History of revascularization of the extremity
10. Current extremity infection
11. Active malignancy*
12. Open fracture / soft tissue injuries
13. Amputation to the lower extremity
14. Expected hospitalization less than 2 weeks on admission
15. Medications known to increase clotting risks
16. Isolation / Contact precaution requirement (e.g. MRSA status, CD toxin +ve status, etc.)

*Active malignancy (Kearon,2016) is defined as follow:

- (1) not received potentially curative treatment; or
- (2) there is evidence that the treatment has not been curative (e.g. recurrent or progressive disease); or
 - A treated cancer is cured should be made by an experienced clinician, with the decision requiring a disease-free interval of follow-up.
- (3) treatment is ongoing.

Standardized 2-week in-patient rehabilitation

- Breathing exercises,
- Bronchial hygiene,
- Health education,
- Bike exercise for 20 minutes (excluding history of hip operation done)
- Walking exercise at least 50m or as tolerated
- Activity of daily living training by Occupational Therapists
- Dietitian referral if needed, to ensure adequate nutrient intake.

A standardized resistance training (Patterson, 2019)

- Exercise: Isotonic knee extension
- Sessions per week: 6 (Except Sunday and public holiday)
- Duration of intervention: 2 weeks
- Total number of sessions during hospitalization: 12 sessions
- Sets per session: 4 (Total Repetitions: 75reps in total across 4 sets)
- Rest between sets: 30s
- Execution speed: 1-2s
- Load: 15-30% of 1 repetition maximum(1-RM) (Loenneke, 2012)

- Involvement of limb per session: Alternate limb training on alternate day
- Execution: until planned rep scheme is completed or contraction failure
- Remarks: If at any time the patient becomes dizzy, severe discomfort (e.g. pain, numbness), training will be stopped.

The BFR-RE intervention group (Patterson, 2019)

The participants will have the above-mentioned resistance training with “BFR-device” with details as follows:

- Cuff size: medium
- Restriction time: 5- 10 mins (stop after finishing 4 sets of training or terminating by Physiotherapists)
- Applied location: alternate quadriceps in consecutive day
- Applied pressure: 80% limb occlusion pressure (LOP)

Control group

Same standardized 2-week in-patient rehabilitation and same amount of the above-mentioned resistance training without the “BFR device”.

Determination of maximal voluntary isometric contraction (MVIC) (Hul, 2004)

- Maximal voluntary isometric contraction (MVIC) is the simplest way to measure the force-producing capabilities of a muscle group objectively during its isometric contraction condition which means muscle group under contraction with a constant velocity of joint motion and muscle length. (The National Isometric Muscle Strength (NIMS) Database Consortium, 1996)
- Computer dynamometer will be used to measure the MVIC of the isometric knee extension of the dominant leg.
- Patient will be seated in hip flexion of 90°, knee flexion of 90°, and the padded force transducer set around malleolus. The lever arm (distance between the force transducer and the point of rotation) will be recorded for calculation of force produced by the computer dynamometer.
- Upper body will be stabilized and verbal encouragement will be given to the participants in a standardized way.
- 3 submaximal warm-up contractions trials will be given with 1-minute rest afterwards.

- 3 trials of MVIC with 1 min of rest between each trial will be instructed. After a build-up phase of 2 s, an MVIC needs to be in a steady, maximal contraction, with a plateau phase of 3 s.
- During measurements, the Physiotherapists can have visual feedback of the force signal, monitoring the quality of the shape of each contraction.
- The highest value for MVIC will be captured for future analysis.

Determination of 1-repetition maximum (1-RM) (Kanada, 2017; Takeichi, 2012)

$1RM \text{ (kg)} = 0.188 + 0.187 \times \text{maximal isometric muscle strength}$. This formula was devised based on examination of 176 in-patient elderlys in Japan (352 legs).

Determination of Hand grip strength (HGS) (Jeong, 2017; Yu, 2017)

- In sitting position with elbow in 90-degree flexion
- Hold dynamometer by the testing hand with the grip meter indicator facing outward, and away from any part of the body.
- Allow 1 practice trial for dominant hand.
- Squeeze the grip with full force and continuously for at least 2 seconds.
- Two trials for handgrip strength test for the dominant hand
- Not to swing the grip dynamometer during the test and not to hold their breaths.
- The time between each trial: ~30s;
- The time interval between trials of the same hand: ~1min
- Verbal encouragement by Physiotherapists.
- HGS will be the average of the reading displayed on the dynamometer in the 2 trials

Determination of limb occlusion pressure (LOP)

- Limb Occlusion Pressure (LOP) is the minimum pressure required, at a specific time in a specific tourniquet cuff applied to a specific patient's limb at a specific location, to stop the flow of arterial blood into the limb distal to the cuff. (Noordin, 2009)
- The 3rd generation tourniquet system features a built-in LOP measurement capability. This allows a personalized tourniquet pressure for each individual patient and eliminated the need to account for cuff width, limb size or blood pressure.

Determination of Leg dominance (Melick, 2017)

Since mobility is a bilateral mobilizing task, the leg dominance will be defined by the participant's preferred leg to shoot a ball when being asked the following question: "If you would shoot a ball on a target, which leg would you use to shoot the ball?"

Determination of completeness of training

80% of the whole course of in-patient additional muscle strength training (i.e. 10 out of 12 sessions)

Determination of acceptance of program

5-point Likert scale will be given to participants after the additional muscle strength training (i.e. very like, like, no comment, dislike, very dislike)

Data collection timepoint

- Baseline
- After completeness of training (i.e. at least 10 sessions of training)

Clinical investigations

- Laboratory tests at baseline and post training program
 - ✧ Clotting profile, Complete blood count (CBC), liver function test (LFT), renal function test (RFT), serum creatinine kinase level (CK), serum lactic acid level, C-reactive protein (CRP)
 - ✧ Estimated 32ml of venous blood in total will be needed for both pre and post training blood tests.
 - ✧ Myoglobin in urine
- Spirometry before discharge of current admission

Primary outcome:

Localized Muscle Strength (Robles, 2011; Hul ,2004)

- Muscle strength is operationally defined as subject's capability for the exertion of force or torque to an external dynamometer over a specified period of time. (Kroemer, 1980)
- Maximal voluntary isometric contraction (MVIC) of knee extension of the dominant leg, with a unit Newton (N), will be assessed by computer dynamometry.

Secondary outcomes:

- **Functional test**
 - ✧ Short physical performance battery (SPPB) (Mora, 2015)
Gait speed with 4m distance, Balance test & repeated chair stands test
 - ✧ 6-minute walk test (Holland, 2010)
- **Systemic muscle strength** (Jeong, 2017; Yu, 2017)
 - ✧ Hand grip strength, a non-invasive marker of systemic skeletal muscle strength and function, is assessed by handheld grip dynamometer of dominant hand
- **Health related quality of life**
 - ✧ Self-administered Chinese version of COPD assessment test (CAT) (Karlah,2016)
- **Acceptability of BFR-RE**
 - ✧ Pain by visual analog scale (0-10) before, immediate and 5-min post exercise
 - ✧ Participant's acceptance by a Likert 5-point categorical scale after the whole program
- **Feasibility of BFR-RE**
 - ✧ Examination of drop-out rate and reasons of drop-out in those discontinuing the training
- **Unplanned readmission rate within 1 month of discharge for COPDAE**

Data analysis

SPSS version 17.0 will be used for statistical analysis.

The comparison of baseline characteristics of subjects across the 2 groups will be tested by independent t-test for continuous variables (e.g. age, anthropologic data, maximum voluntary isometric contraction of knee extension of dominant leg, hand grip strength of dominant hand, laboratory test results, spirometry data, 6-minute walk test, COPD Assessment test (CAT), etc.), Chi-square test for nominal variables (e.g. presence of myoglobin in urine, etc.).

For testing between-group and within-group changes after Blood flow restriction resistance exercise (BFR-RE), multivariate repeated measures ANOVA will be used.

All continuous variables are presented as mean \pm SD (standard deviation). The level of statistical significance was set at $p < 0.05$.

Sample size calculation

A priori power analysis (calculated by G*Power 3.1.9.5) showed that in order to have a power of 80% to detect a difference of medium effect (f^2 : 0.22) of muscle strength gain (Cook, 2017) at the 0.05 level of significance, 18 patients is needed in each group. If a dropout rate of 30% is estimated, 48 patients in total will be needed for the study.

Randomization

Participants are randomized into one of the two treatment groups. A computer compiles randomization list. Based on randomization, envelopes are made with participant number, including allocation of patients to BFR-RE vs. without BFR-RE. The envelopes are opened after inclusion for the individual participant only. The randomization list is kept in a sealed envelope.

Stratification of participants into two groups by maximum voluntary isometric contraction (MVIC) at baseline before randomization will be done. The cutoff for the stratification will be determined from the data in the recent service.

Blinding

Participants, doctors, nurses and involved Physiotherapists are for obvious reasons not blinded, but assessments at recruitment and on discharge will be carried out by blinded Physiotherapists without knowledge of treatment group.

Interruption

The individual participant can withdraw from the study at any time. Participants

may also be excluded from the study at any time based on the investigator's evaluation.

Data registration

All data relevant for the study are recorded in a specific form.

Data of each enrolled participant are listed in a personal form.

Recruitment

Consecutive patients will be recruited in the three pulmonary wards in Haven of Hope Hospital between 10.6.2020 – 28.2.2021. The study will be expected to finish within 9 months or earlier if the expected recruitment achieved.

Expected Benefits

BFR-RE may improve the muscle strength of the knee extension and muscle size of quadriceps in the patients undergoing early rehabilitation for COPDAE. This may allow patients to actively participate the resistance training to improve the mobility function, subsequently health-related quality of life.

Adverse events

In this context, adverse events are defined as any unintended, unfavorable finding, symptom or disease that can be connected to the strength training, whether it is deemed to have a correlation with this or not. Adverse events are recorded by spontaneous registration as well as by open questioning.

Concerns on patient's safety

Delayed onset of muscle soreness (DOMS)

DOMS is normal after exercise, including after LL-BFR training. It was reported in 40% of participants in a survey before but this will subside within 24-72 hours (Patterson, 2018).

Numbness

Incidence of transient numbness is between <2% (Nakajima, 2006) to 18.5% (Patterson, 2018). This is related to the tourniquet pressure causing peripheral nerve compression.

Central vascular response

Continuous BFR-RE (keep restriction during rest period between sets) will

increase the heart rate (HR), systolic blood pressure (SBP), diastolic blood pressure (DBP), or double product (HR x SBP) compared with same exercise in free flow conditions.

Cardiac output is not affected by BFR during exercise since HR increases and stroke volume decreases proportionally compared to non-BFR groups. Changes in central hemodynamic response are blunted after BFR-RE when compared to HL-RE. However, there was reported to be 14.6% of fainting / dizziness related to BFR-RE (Patterson, 2018). The study is not blinded to the physical therapists; thus, the identification of any safety issues will be easy.

Venous thromboembolism (VTE)

The incidence rate of VTE in general population in Asia was 0.2-0.26% (Klatsky, 2000). However, there are minimal adverse events related to this possible complication reported in BFR-RE literature. Most studies use blood markers to assess the risks of VTE BFR-RE. There is no rise in D-dimers, prothrombin fragment, thrombin-antithrombin III complex, C-reactive protein immediately after BFR-RE training or weeks after training (Madarame, 2013). The reported incidence rate of venous thrombus in a large epidemiologic questionnaire (Nakajima, 2006) in Japan was 0.055% and pulmonary embolism was 0.008%.

Moreover, BFR-RE demonstrated a stimulation of fibrinolytic system by increased tissue plasminogen activator (t-PA), a thrombus-degrading protein in the epithelial cells in healthy participants (Nakajima, 2007).

Other vascular concerns (Patterson, 2018)

There are reported superficial thrombophlebitis (0.8%) and subcutaneous hemorrhage (0.8%). Bruising was reported to be 13.1% (Nakajima, 2006).

Rhabdomyolysis

It is a clinical syndrome due to skeletal muscle damage and the release of potentially toxic substances into the circulation. The reported risk was between 0.07-0.2% (Thompson, 2018). The survey (Nakajima, 2006) in Japan revealed the low incidence of 0.008%. However, this risk was not extraordinarily higher than traditional HL-RE training.

Education

Observations and measurements are carried out by physiotherapists,

occupational therapists, doctors associated with the project.

Serious adverse events

In this context, serious adverse events are defined as events or reactions that cause:

- Death
- Life-threatening situations
- Urgent transferal to acute hospital or prolongation of existing hospitalization
- Permanent or severe disability/incapacity

Serious adverse events must be evaluated by the investigator for possible correlations with treatment in the intervention group, to consider whether there is a reasonable possibility that the adverse event has been caused by that.

The following factors are included in the evaluation:

- Consistency of time.
- Conformity with known effects of the treatment.
- Alternative reasons.

If a serious adverse event is considered to have a causal correlation with the treatment, the investigator must consider the study to be terminated ahead of time.

Ethics

The study will be conducted in accordance with the principles of the Helsinki Declaration.

The protocol including patient information and consent forms for the randomized study is approved by the Research Ethics Committee.

The investigator is responsible for informing the Research Ethics Committee of any serious adverse event and/or major changes in the protocol. The coordinating investigator files all correspondence.

During the study period, data will be disclosed to the investigator of the study only. The research data of subjects will be masked with a set of project codes assigned to the subjects. A matching list with subjects' information will be kept away from the project files physically and electronically. Data will be well covered and stored in a locked room when it is not in used or after the study. Electronic data will be encrypted. All study data will be locked in cabinets where the department keeps patient/confidential information. Electronic data will be saved in secured computer of the hospital with restricted access. The

principal investigator will be responsible for its safe keeping. The data will be kept for three years and then discarded following the guideline of HA after completion of storage period.

~ THE END ~

References:

American College of Sports Medicine, ACSM (2009). **American college of sports medicine position stand. Progression models in resistance training for healthy adults.** Med. Sci. Sports Exerc. 41, 687–708. doi: 10.1249/MSS.0b013e3181915670

Brandner, C. R., May, A. K., Clarkson, M. J., & Warmington, S. A. (2018). **Reported Side-effects and Safety Considerations for the Use of Blood Flow Restriction during Exercise in Practice and Research.** Techniques in Orthopaedics, 33(2), 114–121. doi: 10.1097/bto.0000000000000259

Cook, S. B., Laroche, D. P., Villa, M. R., Barile, H., & Manini, T. M. (2017). **Blood flow restricted resistance training in older adults at risk of mobility limitations.** Experimental Gerontology, 99, 138–145. doi: 10.1016/j.exger.2017.10.004

Hicks, R. W., & Denholm, B. (2013). **Implementing AORN Recommended Practices for Care of Patients Undergoing Pneumatic Tourniquet-Assisted Procedures.** AORN Journal, 98(4), 382–396. doi: 10.1016/j.aorn.2013.08.004

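### The 2-week minimum stay in item 14 is counted from admission, but the 12-session course needs 13–14 days from the first session, so a minimum-stay patient has almost no slack

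*Combined protocol and SAP*

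**What the plan says.** The combined protocol and SAP sets the minimum stay in Exclusive criteria, item 14: a patient is excluded for "Expected hospitalization less than 2 weeks on admission". Entry can be by direct hospitalisation or by transfer ("COPD acute exacerbation (COPDAE) as the primary diagnosis for hospitalization or transfer to pulmonary wards of the Haven of Hope Hospital"), and item 14 does not say which admission starts the count for a transferred patient.

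The section A standardized resistance training gives "Sessions per week: 6 (Except Sunday and public holiday"), "Duration of intervention: 2 weeks" and "Total number of sessions during hospitalization: 12 sessions".

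Determination of completeness of training sets the threshold at "80% of the whole course of in-patient additional muscle strength training (i.e. 10 out of 12 sessions"). Data collection timepoint places the only measurement after baseline "After completeness of training (i.e. at least 10 sessions of training"). The Blinding section describes it differently: "assessments at recruitment and on discharge will be carried out by blinded Physiotherapists".

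Several steps must come before the first session. The principal investigator checks fitness and the patient consents (Subjects; Inclusion criteria). Baseline and laboratory data are collected (Data collection timepoint; Clinical investigations). MVIC is measured, because it defines the strata (Randomization) and feeds the 1-RM formula from which the load is set. The documents give no day for the first session, no maximum gap from admission, and no rule for a patient discharged before 10 sessions.

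**The concern.** The same two weeks serve both as the minimum stay and as the length of the course, but the two periods start at different times. Each day between admission and first session comes off the training time of a patient whose stay is at the floor. Such a patient can be eligible and randomised, yet have too few training days left to reach the protocol's own definition of a complete course.

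At stake are avoidable incomplete courses and, if the 10-session timepoint is applied literally, missing post-training MVIC. There is little reserve for this: the sample size section needs 18 per group (36) and plans 48 with 30% dropout, and 48 × 0.7 = 33.6. Drop-out is also a feasibility outcome, so losses caused by the calendar could be read as poor feasibility of the BFR training.

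**Working it through.** **The plan's own figures.** 6 sessions per week × 2 weeks = 12 sessions. 80% of 12 = 9.6, rounded up to 10. Both agree with the protocol.

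**Inputs.** Stay of exactly 14 days with admission as day 1 (the item 14 floor, taken here as the actual stay); no session on Sunday; threshold 10 sessions. Assumptions not in the documents: the day of the first session (varied from 1 to 5), whether day 14 can be a training day (both cases shown), and no public holiday unless stated.

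**Formula.** If the first session is on day *s* and the last possible training day is *T*, the window has L = T − s + 1 days. Number the start weekday *w* from 1 (Monday) to 6 (Saturday). Sundays then fall at positions 8 − w and 15 − w of the window. Possible sessions = L minus the number of these positions that are ≤ L.

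**Length of the course from the first session.** Twelve sessions span 13 days from a Monday start and 14 days from any other. Ten sessions span 11 days from a Monday–Wednesday start and 12 days from a Thursday–Saturday start.

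**Sessions possible in a 14-day stay, no holiday.**

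| First session | Training allowed on day 14 | Day 14 not used for training |
|---|---|---|
| Day 1 | 12 | 12 (Mon), 11 (other days) |
| Day 2 | 12 (Mon), 11 (other days) | 11 (Mon–Tue), 10 (Wed–Sat) |
| Day 3 | 11 (Mon–Tue), 10 (Wed–Sat) | 10 (Mon–Wed), 9 (Thu–Sat) |
| Day 4 | 10 (Mon–Wed), 9 (Thu–Sat) | 9 (Mon–Thu), 8 (Fri–Sat) |
| Day 5 | 9 (Mon–Thu), 8 (Fri–Sat) | 8 (Mon–Fri), 7 (Sat) |

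Worked example for day 4 with T = 14: L = 11. A Wednesday start (w = 3) has Sundays at positions 5 and 12; only the first is ≤ 11, so 11 − 1 = 10. A Thursday start (w = 4) has Sundays at positions 4 and 11, so 11 − 2 = 9.

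**One public holiday on a session day** removes one session. With training allowed on day 14, a day-3 start then reaches 10 only from a Monday or Tuesday, and no day-4 start does. With day 14 not used, no day-3 start reaches 10.

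**Counting from the first session instead.** Fourteen days from any first session contain two Sundays and so 12 training days. If the last of those days is kept free, 11 remain (12 from a Monday start), still above 10.

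**The case against.** The strongest reply has four parts.

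- **Lag.** The lag to first session decides the matter and is not in the documents. The pre-training steps need not take long: MVIC is three short trials with one-minute rests, and nothing bars baseline tests, allocation and first session on the same or the next day. With training allowed on day 14 and no holiday, every start on days 1 to 3 reaches 10. This stands, and is why the number affected cannot be stated.
- **Forecast.** Item 14 is a floor on a forecast, not a discharge date. A shortfall needs a patient expected to stay about 14 days who in fact stays no longer and who starts late. This stands too.
- **Allowances.** The plan already accepts 10 of 12 sessions and allows for 30% dropout. That is true, but the documents do not say whether the allowance was meant to cover patients discharged before session 10.
- **Outcome.** A reader might infer that the rule randomises patients who cannot give a primary outcome. The documents do not support that. The Blinding section has assessment on discharge, which may provide MVIC after fewer than 10 sessions. What remains is that Data collection timepoint ties the measurement to at least 10 sessions, and nothing says which statement governs.

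A reader might also infer that every start on day 4 or 5 fails, or that 12 sessions require a start on the day of admission. Neither holds: a Monday–Wednesday start on day 4 can reach exactly 10, and a Monday start on day 2 still fits 12.

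**Conclusion.** The mismatch of time origins is real and follows from the protocol's own figures. For an actual 14-day stay with no holiday and training allowed on day 14, the 10-session threshold is always reachable from a start on days 1 to 3, reachable from 3 of 6 start weekdays on day 4, and never reachable from day 5. If day 14 is not a training day, day 3 reaches it from only 3 of 6 start weekdays and day 4 never does. One holiday on a session day makes every day-4 start fall short.

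These counts are exact given the stay and the start day, but how often those conditions occur is unknown. For transferred patients it also depends on which admission is meant: if it is admission to the earlier hospital, less time remains. The conclusion is that item 14 does not secure the time the course needs. It does not establish that a material share of patients will be lost. The point is worth correcting because the correction is cheap.

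**What to change.** Reword item 14 so that it is applied at randomisation and counted from the planned first session: exclude if the expected remaining stay from that session is less than 14 days, with one further day for each public holiday in the window (an added day that is itself a Sunday or holiday does not count). State that the post-training assessment must be fitted in before discharge; if it needs a day of its own without training, either accept 11 possible sessions or add a day. Counting from the first session also removes the ambiguity about transferred patients. The training schedule is unchanged.

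Reconcile Data collection timepoint with Blinding: say whether the final assessment is made after at least 10 sessions or on discharge, and whether a patient discharged with fewer than 10 sessions is measured. Record the date of admission and of first session, so that losses from a short stay can be told apart from discontinuation of training.

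The cost is the wording of one criterion and one timepoint, and some short-stay patients become ineligible. For example, a first session on day 4 would imply an expected stay of 3 + 14 = 17 days from admission instead of 14, so recruitment slows slightly. The rule still rests on a forecast, so it reduces early discharges before session 10 but does not eliminate them.

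### Does giving the training load as a range of 15–30% of 1-RM let the two arms train differently and so confound the effect of the cuff?

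*Combined protocol and SAP*

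**What the plan says.** The section on standardized resistance training sets 75 repetitions over 4 sets, 30 seconds of rest and 12 sessions, and then "Load: 15-30% of 1 repetition maximum(1-RM". A set may also end early: "Execution: until planned rep scheme is completed or contraction failure". The Introduction repeats the load range for both arms and describes the control training as the same set without the device. The Control group section promises the "same amount of the above-mentioned resistance training".

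The reference 1-RM comes from a formula applied to maximal voluntary isometric contraction (MVIC). MVIC is measured at baseline, and "Stratification of participants into two groups by maximum voluntary isometric contraction (MVIC) at baseline before randomization will be done".

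Under Blinding, "Participants, doctors, nurses and involved Physiotherapists are for obvious reasons not blinded", while the recruitment and discharge assessments are made by blinded physiotherapists. Completeness of training is defined by sessions: "80% of the whole course of in-patient additional muscle strength training (i.e. 10 out of 12 sessions". Under Data registration, all relevant data go on a study form that is not reproduced in the document. The Data analysis section lists no comparison of delivered load by arm.

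**The concern.** The trial can credit a difference in MVIC to the cuff only if the rest of the training is alike in both arms. Load is the one element of the programme's volume given as a range, and its upper limit is twice its lower limit. No section says who picks the percentage, when it is picked, or whether it changes over the 12 sessions. Staff who deliver the training know the allocation, and a course counts as complete on sessions alone.

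The Introduction ranks strength gains by type of training: "BFR-RE is less effective in gain than that in HL-RE but more effective than that in low load resistance exercise (LL-RE) alone". The safety section adds that "there was reported to be 14.6% of fainting / dizziness related to BFR-RE", which might tempt staff to keep cuffed patients at lighter loads. Blinded outcome assessment would not remove such a difference, because it would arise in how the training was delivered. If load followed allocation, the MVIC comparison would mix two effects, in a direction that cannot be known beforehand.

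**Working it through.** **Inputs.** Load 15–30% of 1-RM, 75 repetitions per session and 12 sessions (standardized resistance training); at least 10 sessions for completeness; 18 per group and f² = 0.22 (Sample size calculation). The plan gives no figure for load by arm. Its one computed figure, used below as the group size, can be reproduced under a two-sided 5% test (sidedness is not stated): d² = 4 × 0.22 = 0.88, so n = 2 × (1.960 + 0.842)² / 0.88 = 17.8, or 18 per group.

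**1. What the range permits between two patients.** Load ratio: 30/15 = 2.0. With every repetition done, 75 × 12 = 900 repetitions, and volume in 1-RM equivalents runs from 900 × 0.15 = 135 to 900 × 0.30 = 270, again 2.0-fold. Setting 10 sessions at 15% (75 × 10 × 0.15 = 112.5) against 12 sessions at 30% (270) gives 2.4. That is 2.0 from load times 12/10 = 1.2 from session count, and the second factor has nothing to do with the load rule.

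**2. What it permits between arm means when load is unrelated to arm.** Assume, for scale, loads spread uniformly over 15–30%.
- SD = 15/√12 = 4.33 percentage points.
- SE of the difference in means, 18 per group = 4.33 × √(2/18) = 1.44 points.
- 95% range = ±1.96 × 1.44 = ±2.8 points, about 13% of the 22.5% midpoint.

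A gap of the full 15 points would be 15/1.44 = 10.4 standard errors. It cannot arise by chance; someone would have to choose load by arm.

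**3. Would choosing load by arm be consistent with the plan?** The Introduction and the Control group section both describe the control training as identical apart from the device. Training one arm at the bottom of the range and the other at the top would contradict both. The reference 1-RM is also protected: it derives from baseline MVIC, which is measured by blinded assessors and is known before allocation because it is the stratification factor. Only the percentage applied to it is left unwritten.

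**4. Is there a documented reason for unequal loads?** The stated response to dizziness, or to severe discomfort such as pain or numbness, is to stop the training, and it applies to both arms. Lowering the load is not mentioned. Numbness is attributed to cuff pressure, not to load. Lighter loading of cuffed patients is therefore conjecture.

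**5. Would load within this range move MVIC?** The Introduction's ranking compares high load, restricted flow and low load. The step from low load alone to restricted flow is a contrast in the cuff, not in load. The Introduction puts the load needed for muscle growth at 70% of 1-RM or more; 15% and 30% are 15/70 = 0.21 and 30/70 = 0.43 of that. The documents give no dose–response between 15% and 30% over two weeks.

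**6. What a bias would do, if there were one.** With 18 per arm, a two-sided 5% t-test (34 degrees of freedom, noncentrality = shift × √(18/2)) would reject a true null 6.0%, 9.0% or 14.1% of the time for shifts of 0.1, 0.2 or 0.3 SD. These shifts are assumed. No figure in the documents links a load difference to any of them, so they describe any bias of that size and are not evidence of one here.

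**The case for a change.** The strongest case is that intent is not procedure. The plan says the training is the same but provides nothing to secure or verify this: no stated rule for placing a patient in the range, no named entry for delivered load, and no table by arm, while the staff giving the training know who wears the cuff. Session loads that are not written down cannot be recovered afterwards, and writing them down would cost almost nothing.

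The factual part stands: the rule and the form entry are not stated. The rest is inference. That treating staff choose the load, and do so after allocation, is plausible but nowhere written. That load goes unrecorded is not shown either, because the form is not in the document and is said to hold all relevant data. The protocol also cites outside sources for the training and for the load, and these cannot be consulted here. Finally, if load varies between patients but not with allocation, it adds spread to both arms without biasing the comparison.

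**Conclusion.** No change to the plan is needed. The point is a missing working detail, not a rule or figure shown to give a wrong result. The load range is common to both arms, the plan commits to identical training apart from the device, and the 1-RM it refers to rests on a blinded measurement made before allocation. The ordinary way to carry this out is to set load in the same manner for everyone and note it on the training form; nothing in the text points the other way.

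On size: 2.0-fold is the limit between two patients at equal repetitions. The chance difference between arm means is about ±2.8 percentage points with 18 per group, assuming a uniform spread unrelated to arm. The conclusion rests on reading the same-training wording in its plain sense and on the absence of any figure in the documents linking load within 15–30% to MVIC. It would need revisiting if delivered loads proved to differ clearly by arm. No view is taken on which load is right.
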